Blood creatinine increased	
Grade 3 (>3.0 to <math>6.0 \times \text{ULN}</math>)	Delay dose until resolved to $\leq$ Grade 2 or Baseline, then reduce dose 1 level
Grade 4 (>6.0 $\times$ ULN)	Discontinue subject from study treatment

Hepatic Toxicity	
Aspartate Aminotransferase (AST) or Alanine Aminotransferase (ALT) with Simultaneous total Bilirubin (TBL)	
AST/ALT $\geq 3.0 \times$ ULN with simultaneous TBL $> 2.0 \times$ ULN	
Delay study medication until drug-induced liver injury can be ruled out.
 
If drug-induced liver injury is ruled out, the subject should be treated accordingly, and resumption of study drug may occur after discussion between the Investigator and the Sponsor.
 
If drug-induced liver injury cannot be ruled out from diagnostic workup, permanently discontinue study treatment.
 
Monitor AST/ALT and TBL twice weekly until resolution or return to baseline.

Aspartate Aminotransferase (AST) or alanine Aminotransferase (ALT)	
Grade 2 ( $>3.0$ to $5.0 \times$ ULN )	No action for Grade 2 AST/ALT
Grade 3 : $>5.0$ to $20.0 \times$ ULN. In subjects without liver metastases and subjects with liver metastases and baseline level $\leq 3 \times$ ULN	
Repeat testing within 3 days. Delay dose until resolved to <math>\leq</math> Grade 1 if baseline <math>\leq 3 \times</math> ULN, otherwise delay dose until resolved to <math>\leq</math> baseline, then:
 
 
• If resolved in <math>\leq 7</math> days from day of onset, maintain dose
 
• If resolved in <math>>7</math> days from day of onset, reduce dose 1 level
 

Grade 3: $>8.0$ to $20.0 \times$ ULN) In subjects with liver metastases, if the baseline level was $>3 \times$ ULN	
Repeat testing within 3 days. Delay dose until resolved to <math>\leq</math> baseline level, then:
 
 
• If resolved in <math>\leq 7</math> days from day of onset, maintain dose
 
• If resolved in <math>>7</math> days from day of onset, reduce dose 1 level
 

Grade 4 ( $>20 \times$ ULN )	Discontinue subject from study treatment
Total Bilirubin (TBL)	

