Grade 2 ( $>1.5$ to $3.0 \times$ ULN )	
If no documented Gilbert's syndrome or liver metastases at baseline, delay dose until resolved to <math>\leq</math> Grade 1:
 
 
• If resolved in <math>\leq 7</math> days from day of onset, maintain dose
 
• If resolved in <math>>7</math> days from day of onset, reduce dose 1 level
 
 
If documented Gilbert's syndrome or liver metastases at baseline, continue study treatment

Grade 3 ( $>3.0$ to $10.0 \times$ ULN )	
If no documented Gilbert's syndrome or liver metastases at baseline, repeat testing within 3 days. Delay dose until resolved to <math>\leq</math> Grade 1:
 
 
• If resolved in <math>\leq 7</math> days from day of onset, reduce dose 1 level
 
• If resolved in <math>>7</math> days from day of onset, discontinue DS-8201a
 
 
If documented Gilbert's syndrome or liver metastases at baseline, repeat testing within 3 days. Delay dose until resolved to <math>\leq</math> Grade 2:
 
 
• If resolved in <math>\leq 7</math> days from day of onset, reduce dose 1 level
 
• If resolved in <math>> 7</math> days from day of onset, discontinue DS-8201a
 

Grade 4 ( $>10.0 \times$ ULN)	Discontinue subject from study treatment
Blood Alkaline Phosphatase (ALP) Increased	
Grade 3 or 4 ( $>5.0 \times$ ULN)	No modification unless determined by the Investigator to be clinically significant or life-threatening.
Gastrointestinal	
Nausea	
Grade 3	
Delay dose until resolved to <math>\leq</math> Grade 1
 
 
• If resolved in <math>\leq 7</math> days from day of onset, maintain dose
 
• If resolved in <math>>7</math> days from day of onset, reduce dose 1 level
 

Diarrhea/Colitis	
Grade 3	Delay dose until resolved to $\leq$ Grade 1

	
 
• If resolved in <math>\leq 3</math> days from day of onset, maintain dose
 
• If resolved in <math>> 3</math> days from day of onset, reduce dose 1 level
 

Grade 4	Discontinue subject from study treatment
Other Laboratory Adverse Events	

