#### **8.5. Serious Adverse Events Reporting-Procedure for Investigators**

All AEs, SAEs and AESIs, and medication errors including overdose will be reported in the eCRF.

Serious events that are also efficacy endpoints (eg, PD) and/or safety endpoints will be exempted from SAE processing and expedited reporting. Disease progression should not be reported as an AE/SAE. However, when a subject dies from PD with no other immediate causes, “disease progression” should be reported as an SAE and captured on designated eCRF. These events are clinically anticipated events in the target treatment population, and will be periodically reviewed by the Daiichi Sankyo safety teams to ensure prompt identification of any clinically concerning safety issues.

The following types of events should be reported by the Investigator in electronic data capture (EDC) within 24 hours of awareness. A treatment-emergent adverse event (TEAE) is defined as an AE that occurs, having been absent before the first dose of study drug, or has worsened in severity or seriousness after the initiating the study drug until 47 days after last dose of the study drug. SAEs with an onset or worsening 48 days or more after the last dose of study drug, if considered related to the study treatment, are also TEAEs.

- SAEs (see Section 8.4.2 for definition)
- All potential ILD cases should be reported within 24 hours; including both serious and non-serious potential ILD cases (potential ILD is defined by the Event Adjudication Site Manual List of PTs).

- Hepatic events (both serious and non-serious) which meet the potential Hy's Law criteria defined as an elevated (ALT or AST)  $\geq 3 \times$  ULN and an elevated TBL  $> 2 \times$  ULN that may occur either at different time points or simultaneously during the study conduct. A targeted questionnaire is in-built within the eCRF to collect relevant additional information for these potential cases.
- Overdose, defined as the accidental or intentional administration of any dose of a product that is considered both excessive and medically important. An "excessive and medically important" overdose includes any overdose in which either a serious adverse event, a non-serious adverse event, or no adverse event occurs and is considered by the Investigator as clinically relevant, i.e. poses an actual or potential risk to the subject.

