Overdose is always serious. By definition an overdose is medically important, which meets the seriousness criterion of important medical event. An overdose can occur with or without an AE. AEs can either be serious or non-serious. Details of the overdose including trastuzumab deruxtecan dosage, clinical course, associated AEs, and outcome must be captured in the Narrative form of the CRF within eDC. Disease progression/worsening of primary cancer (gastric, gastroesophageal junction [GEJ] adenocarcinoma, or breast cancer) will not be recorded as an AE on the Adverse Event eCRF. However, events associated with disease progression may be recorded as AEs.

Death due to disease progression should be recorded on the Death eCRF.

All events (serious and non-serious) must be reported with Investigator's assessment of the event's seriousness, severity, and causality to the study drug. A detailed narrative summarizing the course of the event, including its evaluation, treatment, and outcome should be provided. Specific or estimated dates of event onset, treatment, and resolution should be included when available. Medical history, concomitant medications, and laboratory data that are relevant to the event should also be summarized in the narrative. For fatal events, the narrative should state whether an autopsy was or will be performed, and include the results if available. Source documents (including medical reports) will be retained at the study site and should not be submitted to the Sponsor for SAE reporting purposes.

Urgent safety queries must be followed up and addressed promptly. F/U information and response to non-urgent safety queries should be combined for reporting to provide the most complete data possible within each F/U.

Please call the local SAE Hotline (see Study Manual) or your study monitor for any questions on SAE reporting.

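### Table 5.2 requires drug-induced liver injury to be ruled out before redosing only for simultaneous AST/ALT and bilirubin rises, so a staggered case reportable under Section 8.5 as potential Hy's Law carries no such requirement

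*Combined protocol and SAP*

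**What the plan says.** Section 8.5 lists hepatic events, serious or not, among those the investigator must enter in the EDC system within 24 hours. The trigger is AST or ALT at least 3 times ULN together with total bilirubin (TBL) above 2 times ULN, "that may occur either at different time points or simultaneously during the study conduct". It attaches a targeted questionnaire and, as for every reported event, the investigator's view of "seriousness, severity, and causality to the study drug". It gives no dosing instruction and no time limit between the two values.

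Dosing is governed by Table 5.2. Its first hepatic block is headed AST or ALT "with Simultaneous total Bilirubin (TBL") and uses the same two thresholds. The instruction is "Delay study medication until drug-induced liver injury can be ruled out", with resumption only after the investigator and sponsor have discussed it and with twice-weekly monitoring. The block adds: "If drug-induced liver injury cannot be ruled out from diagnostic workup, permanently discontinue study treatment". It does not define how close in time two values must be to count as simultaneous.

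The remaining hepatic rows treat AST/ALT and TBL separately, by grade and time to resolution. For AST/ALT above 3 and up to 5 times ULN the entry is "No action for Grade 2 AST/ALT". For TBL above 1.5 and up to 3 times ULN, subjects with documented Gilbert's syndrome "or liver metastases at baseline, continue study treatment".

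**The concern.** The two sections agree on the thresholds that mark possible serious liver injury but not on timing. The same pair of values stops dosing until liver injury is excluded if both fall on one draw. If they fall on different draws, the pair is still reportable as potential Hy's Law, yet the dosing decision reverts to rows that look at one analyte at a time.

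At stake is whether a subject can be redosed before anyone has had to consider liver injury as an explanation for the pair. Section 1.4 accepts that hepatotoxicity may occur with this drug. The simultaneous row makes no exception for Gilbert's syndrome or liver metastases, so the sponsor already wants the rule-out in those subjects when the values coincide.

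**Working it through.** The plan has no figure to reproduce here. The check is a trace of staggered values through the hepatic rows of Table 5.2. *Simultaneous* is read as the same draw, which is an assumption. In the staggered cases, the analyte not named is below its threshold at that draw.

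| Case | Values | Table 5.2 outcome | Liver-injury assessment required before redosing? |
|---|---|---|---|
| A | ALT 4× and TBL 2.5× ULN on one draw | Hold; stop permanently if injury cannot be ruled out | Yes |
| B | ALT 4×, then TBL 2.5×; Gilbert's syndrome or liver metastases, baseline AST/ALT ≤3× | AST/ALT row: no action. TBL row: continue | No; dosing uninterrupted |
| C | As B, with neither condition | TBL row: hold to Grade 1 or lower; same dose if resolved in ≤7 days, otherwise one level lower | No |
| D | ALT 6× (baseline ≤3×), then TBL 2.5× | AST/ALT row: retest within 3 days, hold to Grade 1 or lower; same dose if ≤7 days, otherwise one level lower. Then the TBL row as in B or C | No |
| E | ALT 4×, then TBL 4× | TBL row: retest within 3 days, hold; one level lower if resolved in ≤7 days, otherwise discontinue | No |
| F | Any AST/ALT >20× or TBL >10× | Discontinue | Not applicable |

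Cases A to E all meet the Section 8.5 definition; only A triggers the rule-out. B is the only one of them in which dosing is never interrupted.

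A further group is set aside. A separate Grade 3 row applies "In subjects with liver metastases, if the baseline level was" above 3 times ULN. In these subjects a staggered pattern needs the enzyme to be below 3 times ULN, hence below the subject's own baseline, at the draw where TBL exceeds 2 times ULN. That group is close to empty.

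Sections outside Table 5.2 that might close the gap:

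- Section 5.4.1 requires the investigator to decide which toxicities are attributable to the drug, but the dose adjustment that follows is the one recommended in Table 5.2. Its further provision on reduction or discontinuation, repeated under the table, is optional.
- Section 8.8 requires laboratory values to be assessed and acted on, without naming a rule-out.
- The causality assessment in Sections 8.4.4 and 8.5 is a reporting step.
- The safety monitoring team (Section 11.7) meets when necessary, with no link to redosing.

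None makes redosing conditional on a liver-injury assessment.

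Draw spacing matters for the fix. From Cycle 4, scheduled chemistry is on Day 1 only (Section 6.3.15.1 and Table 17.3), from a sample up to 3 days before dosing. Two consecutive on-schedule draws are nominally 21 days apart and at most 21 + 3 = 24 days apart.

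**The case against.** A reporting trigger may properly be wider than a dosing trigger, particularly one with no time limit. The plan also protects staggered cases more than a quick reading suggests. Grade 4 values discontinue, Grade 3 bilirubin lasting more than 7 days discontinues, Grade 3 AST/ALT or bilirubin is retested within 3 days, and Section 5.4.1 requires monitoring of Grade 3 and 4 events at least every 7 days. The AST/ALT and bilirubin rows can each remove a dose level. All of this stands, and it makes the gap narrow.

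Simultaneous has no defined window, so an investigator could apply that row to values a few days apart. That is possible. However, Section 8.5 sets different time points against simultaneous, which points to the narrower reading, and the ambiguity is itself a reason to clarify.

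Three stronger readings are tempting and not supported:

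- **Staggered cases go unmanaged.** They do not; only the liver-injury assessment is missing.
- **Day 1-only draws from Cycle 4 will make staggered patterns common.** Chemistry is one panel. If both rises begin between two draws, the next draw shows them together or shows only one. A staggered pattern needs one analyte above its threshold at one draw and below it at the draw where the other is raised.
- **Counting the Table 5.2 combinations that allow redosing measures the problem.** Such a count weights unlike situations equally and says nothing about how often they occur.

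**Conclusion.** The mismatch is real and narrow. No row of Table 5.2 requires a liver-injury assessment before redosing when the two thresholds are crossed on different draws, although Section 8.5 treats that case as potential Hy's Law. Uninterrupted dosing is possible mainly in case B; in the other staggered combinations traced, dosing is held or stopped for other reasons. No rate is given in the documents and about 12 subjects are planned, so no expected number of cases can be stated.

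The conclusion rests on reading simultaneous as the same draw and concerns rises close in time. If sites read it as the same clinical episode, the gap shrinks and the added row only records existing practice.

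This is an inexpensive subject-safety improvement for the sponsor to consider. A reader might infer that the safety or efficacy results are compromised. They are not: no endpoint, analysis set or estimate depends on it. A reader might also infer that staggered cases should carry the same mandatory permanent discontinuation as simultaneous ones. The documents do not settle that; it is a medical trade-off, because it could take a benefiting subject off treatment.

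**What to change.** Leave Section 8.5 unchanged. In Table 5.2, directly below the simultaneous row, add:

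> AST/ALT ≥3.0 × ULN and TBL >2.0 × ULN, each above the subject's baseline, on different draws within a window set by the sponsor's medical team (eg, 28 days): withhold the next dose until the Investigator has documented a drug-induced liver injury assessment and discussed resumption with the Medical Monitor. The single-analyte rows continue to apply as a minimum.

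The above-baseline condition is needed because inclusion criterion 5 admits subjects with liver metastases at AST/ALT up to 5 times ULN, and subjects with liver metastases or Gilbert's syndrome at TBL below 3 times ULN. A 28-day window spans two consecutive on-schedule Day 1 draws (at most 24 days apart). A delayed dose, allowed up to 49 days after the previous one, can put draws further apart, so the window is a medical choice. Values outside it would remain reportable under Section 8.5 only.

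Do not add automatic permanent discontinuation for staggered cases; leave that to the Investigator and Medical Monitor.

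The cost is one table row by amendment and, per case, one documented assessment, one discussion and a possible short dose delay.

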## **8.6. Notifying Regulatory Authorities, Investigators, and Institutional Review Board/Ethics Committee**

Daiichi Sankyo and/or CRO will inform Investigators, IRBs, and regulatory authorities of any Suspected Unexpected Serious Adverse Reactions (SUSARs) occurring in other sites as appropriate per local reporting requirements. Daiichi Sankyo and/or CRO will comply with any additional local safety reporting requirements.

In Taiwan, upon receipt of the Sponsor's notification of SUSARs, it is the Investigator's responsibility to report all SUSARs to the IRB according to the reporting guideline of the IRB.

### 8.7. Exposure in Utero During Clinical Studies

Daiichi Sankyo must be notified of any subject who becomes pregnant while receiving or within 4 months of discontinuing the study drug.

Although pregnancy is not technically an AE, all pregnancies must be followed to conclusion to determine their outcome. This information is important for both drug safety and public health concerns. It is the responsibility of the Investigator, or designee, to report any pregnancy in a female subject or a partner of male subject using the Exposure in Utero (EIU) Reporting form, within 24 hours of learning of the pregnancy. Please contact your study monitor to receive the EIU Reporting form upon learning of a pregnancy. The Investigator should make every effort to follow the subject or partner until completion of the pregnancy and complete the EIU Reporting form with complete pregnancy outcome information, including normal delivery and induced abortion. The adverse pregnancy outcome, either serious or non-serious, should be reported in accordance with study procedures. If the outcome of the pregnancy meets the criteria for immediate classification as an SAE (ie, post-partum complications, spontaneous or induced abortion, stillbirth, neonatal death, or congenital anomaly, including that in an aborted fetus), the Investigator should follow the procedures for reporting SAEs outlined in Section 8.5.

### 8.8. Clinical Laboratory Evaluations

Blood samples for laboratory evaluations will be collected according the time points indicated in the schedule of events (Table 17.3).

Instructions for the handling and shipping of blood samples are included in a separate document (eg, laboratory manual).

The following clinical laboratory tests will be performed:

Laboratory tests	Parameters
Hematology	Red blood cell count, Hb, hematocrit, platelet count, white blood cell count, differential white blood cell count (neutrophils, lymphocytes, monocytes, eosinophils, basophils)
Chemistry	Total protein, albumin, ALP, ALT, AST, TBL, troponin, blood urea nitrogen, calcium, chloride, serum creatinine, lactate dehydrogenase, potassium, sodium, and magnesium
Urinalysis	Protein, blood, gravity, glucose, PH, ketone, nitrite, leukocyte esterase, urobilinogen, bilirubin, color, clarity/turbidity

In addition, the following parameters will be analyzed at the visits indicated in appendix Section 17.6.

- Pregnancy test (serum or urine) for all female subjects of childbearing potential must be performed during the Screening Period. A positive urine pregnancy test result must be confirmed immediately using a serum test.

All laboratory values must be assessed by the Investigator as to clinical significance and used to take appropriate clinical management measures. All abnormal laboratory values considered clinically significant by the Investigator should be recorded on the AE page of the eCRF. If the abnormal laboratory value constitutes an SAE, a SAE information should be reported according to the procedures (see Section 8.5). Abnormal laboratory values (NCI-CTCAE Grade 3 or 4) occurring during the clinical study will be followed until repeat test results return to normal (or Baseline), stabilize, or are no longer clinically significant.

### **8.9. Vital Signs**

Vital sign evaluations will be performed according to the time points indicated in the schedule of events (Table 17.3).

Vital sign measurements will include systolic and diastolic blood pressure, pulse rate, respiratory rate and body temperature. Additionally, SpO2 will be measured before administration on Day 1 of each cycle and EOT.

### **8.10. Electrocardiograms**

ECG evaluations will be performed according to the time points indicated in the schedule of events (Table 17.3).

Standard supine 12-lead ECGs in triplicate will be performed in the schedule of events (Table 17.3). Standard ECG parameters will be measured, including RR, PR, QT intervals, and QRS duration. All ECGs must be evaluated by the Investigator or delegated physician for the presence of abnormalities.

### **8.11. Physical Examinations**

Physical examinations will be performed according to the time points indicated in the schedule of events (Table 17.3).

Physical examination findings will include the following body systems/organs: general appearance; dermatological; head and eyes; ears, nose, mouth, and throat; pulmonary; cardiovascular; abdominal; genitourinary (optional); lymphatic; musculoskeletal/extremities; and neurological. Weight and height will also be recorded in kilograms and centimeters, respectively.

### **8.12. Other Examinations**

Other evaluations such as ECHO or MUGA, ECOG PS, and ophthalmologic assessments will be performed according to the time points indicated in the schedule of events (Table 17.3).

LVEF will be measured by either ECHO or MUGA. Ophthalmologic assessments will include visual acuity testing, slit lamp examination, funduscopy testing. All ECHOs or MUGAs, and the ophthalmologic assessments must be evaluated by the Investigator or delegated physician.

#### Pulmonary Assessments

- Pulmonary assessment will include CT or MRI of the chest, SpO2 and will be performed as described in schedule of events. For more details please refer to Section 6 of the protocol.
- An ILD AC will review all cases of ILD on an ongoing basis. Description of the ILD AC is available in Section 8.3.1 .

Additional safety assessments should be conducted as needed, at the Investigator's discretion.

## **9. EFFICACY ASSESSMENTS**

### **9.1. Assessments for Efficacy Endpoints**

Efficacy assessments will be based on tumor assessments. The same imaging tumor assessment as at Screening by CT or MRI scans will be performed every 6 weeks ( $\pm 7$  days) in the first 24 weeks after Day 1 of Cycle 1 and thereafter every 12 weeks ( $\pm 7$  days) regardless of the delay in dosing. The clinical activity of DS-8201a will be assessed by evaluating tumor response. Tumor response will be evaluated using RECIST version 1.1 (Section 17.4).

CT or MRI (spiral CT or MRI with  $\leq 5$  mm cuts) of the brain, chest, abdomen, and pelvis should be used for tumor assessments unless another modality of disease assessment is necessary for the lesions at Screening. Every effort should be made to use the same assessment modality for all assessments for each subject. However, if there is no brain metastasis at Screening, CT or MRI should only be done when symptoms associated with brain metastasis occur during study period. If no clinical symptoms are observed, brain CT or MRI is not mandatory during study period.

The following efficacy endpoints will be assessed. The efficacy variable(s) will be also evaluated at 18 weeks after Day 1 of Cycle 1:

- ORR (the sum of complete response [CR] rate and partial response [PR] rate)
- DCR (the sum of CR rate, PR rate, and SD rate)
- DoR
- PFS
- OS
- Best percentage change in the sum of diameter(s) of target lesion(s)

